13.17 Biospecimen Collection, storage and transport

Please see the Biospecimen Collection protocol for details of sample collection and transport. The use of a barcode identifier linked to the EMT2 trial participant number and date of the sample means that all samples will be stored, transported and analysed in an anonymised but linked manner.

13.18 Adverse Events and Serious Adverse Events

Adverse Events (AEs) and Adverse Reactions (ARs) will be collected at all trial clinic visits and by 2-weekly telephone calls between visit 1 and visit 2 and at 60 days post visit 10/exit visit. AEs and ARs will be collected on the CRFs. These should be reported via the standard data management routes and expedited reporting is not required.

Serious Adverse Events (SAEs), Serious Adverse Reactions (SARs) and Suspected Unexpected Serious Adverse Reactions (SUSARs) will be collected from randomisation until 60 days after the last trial IMP was taken.

For all SAEs, SARs and SUSARs occurring in the trial, an SAE or SAR Report CRF must be completed and faxed or sent via secure email to the CTRU **within 24 hours** of the site becoming aware of the event (see Pharmacovigilance Section 14).

Please see Appendix B for details on the Pharmacovigilance reporting procedures.

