12.2.4. Dose reduction

Participants should be advised to contact the relevant research nurse between the 6-monthly clinic visits/telephone calls in the event of a persistent AE that may require capsule dose reduction.

In the event that the participant experiences AEs that the treating clinician suspects to be related to trial treatment, the clinician should review the participant's treatment regimen (eg. have the capsules been taken with food?).

[figure not shown]
If the AE persists, the dose of trial treatment should be temporarily reduced as per the dose reduction algorithm in Figure 1 below. Dose reduction should be recorded in the medical notes and on the Treatment CRF.

If a participant is undergoing a course of chemotherapy and a dose reduction has stopped the symptoms of an AE, the dose should not be increased back to full dose until the course of chemotherapy has completed.

If a participant is undergoing a course of chemotherapy and has stopped taking trial capsules due to an AE (i.e. is on a treatment break), the participant should resume on the reduced dose once the course of chemotherapy has completed with a view to increasing the capsule dose to 4 capsules daily, in due course. A decision to permanently stop trial treatment should not be made during chemotherapy if possible.

If a participant is still experiencing symptoms of the AE following a dose reduction, is not undergoing a course of chemotherapy and no other factors are considered to be contributory, a permanent halt to trial treatment should be considered. If a participant does permanently stop trial treatment, a Withdrawal CRF should be completed and returned to CTRU within 24 hours. The participant should continue to attend trial visits or take a trial specific telephone call as per the trial visit schedule.

Figure 1: Dose reduction algorithm

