12.4 Withdrawals

In line with usual clinical care, cessation or alteration of regimens at any time will be at the discretion of attending clinicians or the participants themselves. All participants withdrawn from treatment or prescribed alternative treatment will still attend for follow-up assessments unless unwilling to do so and CRFs will continue to be completed.

The Withdrawal CRF should be completed and faxed or sent via secure email to the CTRU **within 24 hours** of the research team becoming aware.

Treatment breaks are permitted if necessary (see Section 12.2.1). Participants should not be recorded as withdrawn from trial treatment until it is clear that they will not be resuming trial treatment.

The PI or delegate should make every effort to ensure that the specific wishes of any participant who wishes to withdraw consent for further involvement in the trial are defined and documented using the Withdrawal CRF in order that the correct processes are followed by the CTRU and site following the withdrawal of consent.

It should be made clear to any participant specifically withdrawing consent for further data collection that data pertaining to safety will continue to be collected for regulatory reporting purposes and will be included in any safety analysis. In addition it is suggested that the participant is made aware of the fact that if any significant new information becomes available in regard to the treatment they have received in the trial it may be necessary to contact them in the future.

In the event that the liver metastases are not able to be removed surgically, trial treatment and follow-up should continue as per protocol (see section 13.4).

13. Assessments, Samples and Data Collection

Data will be collected using paper CRFs, the electronic templates for which will be provided by the CTRU and upon completion should be returned to the CTRU at the University of Leeds. Participating hospitals will be expected to maintain a file of essential trial documentation (Investigator Site File), which will be provided by the CTRU, and keep copies of all completed CRFs for the trial in the Investigator Site File.

The timings of interventions and assessments required for the EMT2 trial are summarised in Appendix A: Schedule of Events.

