13.6 Visits 4-6: Treatment Assessments and Data Collection

Participants will have a trial visit at 12, 18 and 24 months (+/- 2 weeks) after the date of CRCLM surgery. The following assessments will be carried out at each visit:

- Clinical evaluation to assess for disease progression and new primary cancer, as per local standard practice.
- Toxicity assessment: collection of any adverse events which may have occurred since the last trial visit.

- Details of hospital resource activity (e.g. hospital inpatient stays, outpatient clinics attending, accident and emergency attendances).
- Participant self-reported assessments: the EQ-5D, EORTC QLQ-C30 and QLQ-LMC21 Quality of Life questionnaires and a health economics questionnaire will be administered to the participant in a Participant Questionnaire Visit 3-10 Pack. Questionnaires should be completed by participants at the time of clinical/telephone assessment, but before discussion of the outcome of any medical assessments or blood tests wherever possible.
- Participants should be provided with a Participant Diary Booklet to record information over the next visit period. The information collected in the booklet will be the information to be collected in the health economics questionnaire and details on compliance and adverse events. The booklet is intended to act as a reminder to the participant and must not be handed in to clinic or returned to the CTRU.
- Weight in kilograms (in light indoor clothing and without shoes).
- CT scan of thorax, abdomen and pelvis.
- Treatment compliance: the participant will be asked if they have missed any treatment doses since the last trial visit and for what reason.
- Details of concomitant medications including over-the-counter O3FA supplements in since the last trial visit. Participants should be reminded that over-the-counter O3FA supplements are prohibited.
- One box of IMP will be dispensed.
- The IMP dispensed at the previous visit should be checked regarding the expiry date and the participant should be advised to use the IMP box currently in use before opening the IMP box dispensed at this visit/telephone call.
- See Biospecimen Collection protocol if participant is already in this sub-study. A sample collection pack may need handing /posting to the participant at visit 5.

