14.3.1 Reporting of Adverse Events (AEs)

All AEs occurring **from randomisation up to 60 days after the end of trial treatment** must be recorded on the appropriate CRF. These are not subject to expedited reporting to CTRU.

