19.5 Secondary endpoint analysis

Kaplan-Meier survival curves will be calculated for Overall Survival (OS). Participants without an OS event at the time of analysis will be censored at the time they were last known to be alive. Differences in OS between the treatment groups will be compared using multivariate

modelling (for example, an extended Cox model if appropriate) to adjust for the minimisation factors and regular aspirin use during follow-up, which will be included as a time dependent covariate, and subsequent analyses will be conducted to examine the effects of other potential effect modifiers in addition to the minimisation factors. Treatment HRs and corresponding 95% confidence intervals will be obtained from the multivariate models.

Safety analyses will summarise the AE, AR, SAE, SAR and SUSAR rates per participant, by treatment received and overall. Suspected relationship to IPE will be presented along with other causality, outcome and event duration.

QoL will be measured using the general EQ-5D and cancer specific EORTC QLQ-C30 and QLQ-LMC21 questionnaires. These will be analysed using random effects (multi-level) models to account for the hierarchical nature of repeated measures data and the models will include adjustments for baseline QoL, the minimisation factors and regular aspirin use during follow-up, which will be included as a time dependent covariate, with subsequent sensitivity analyses to adjust for any other potential effect modifiers in addition to the minimisation factors. The nature of any missing data will be investigated and if it is suspected that data are not missing at random alternative analyses will be carried out to allow for the nature of the missing data.

The number and timing of new primary cancers will be summarised descriptively by treatment group.

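### AE and SAE collection windows conflict between 13.18, the visit lists and 14.3, and rates per participant would then mislead if stopping of IMP differs between arms

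*Protocol*

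**What the plan says.** **Collection.** Section 13.18 says that AEs and ARs "will be collected at all trial clinic visits and by 2-weekly telephone calls between visit 1 and visit 2", and again 60 days after visit 10. The visit lists in 13.5 to 13.8 repeat the instruction, for example "Toxicity assessment: collection of any adverse events which may have occurred since the last trial visit", and Appendix A marks an AE assessment at each of these visits. None of these places sets a limit for participants who are off IMP. For SAEs, SARs and SUSARs, 13.18 says that they "will be collected from randomisation until 60 days after the last trial IMP was taken".

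**Reporting.** Section 14.3.1 requires AEs to be recorded "from randomisation up to 60 days after the end of trial treatment", and 14.3.2 sets the same period for ARs. For SAEs, the opening of 14.3 counts the 60 days from cessation of trial treatment; 14.3.3 and 14.3.4 count them from its end.

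**Stopping and breaks.** After a permanent stop, 12.2.4 says: "The participant should continue to attend trial visits or take a trial specific telephone call as per the trial visit schedule". On breaks, 12.4 says: "Participants should not be recorded as withdrawn from trial treatment until it is clear that they will not be resuming" trial treatment. Section 12.2.1 sets no maximum length for a break.

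**Analysis.** Section 19.5 says: "Safety analyses will summarise the AE, AR, SAE, SAR and SUSAR rates per participant, by treatment received and overall". By 19.2 the safety population is everyone who took at least one dose. No person-time denominator is mentioned.

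**The concern.** There are two linked problems.

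First, the instructions do not agree on what is collected once a participant is off IMP. A site that works from the visit lists keeps asking about AEs for as long as the participant attends. A site that works from 14.3.1 stops 60 days after treatment ends. The contents of the safety tables then depend partly on which section a site follows.

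Second, the SAE observation period is tied to staying on IMP. Stopping happens after randomisation, can be prompted by adverse events (12.2.4), and so may differ by arm. If it does, a count divided by participants mixes the event rate with the length of time during which events were collected. The arm that stops more would look safer on SAEs even with identical true rates. Safety and tolerability, including during chemotherapy, is a stated secondary objective (7.3), and chemotherapy is one of the situations in which the protocol foresees breaks.

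**Working it through.** **1. The windows side by side**

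| Event | 13.18 and visit lists | 14.3 and subsections |
|---|---|---|
| AE, AR | every trial visit, no off-treatment limit | to 60 days after end of treatment (14.3.1, 14.3.2) |
| SAE | to 60 days after last IMP taken (13.18) | to 60 days after cessation or end of treatment (14.3, 14.3.3) |
| SAR, SUSAR | as SAE | as SAE, but later ones that the site learns of are still reported (14.3.4) |
| Death | not applicable | recorded throughout follow-up (13.20) |

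The AE row is a direct conflict. The last two rows limit the damage: what can be lost is mainly the unrelated, non-fatal SAE.

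**2. The SAE clock during a break.** Put the last capsule at day 0 and an SAE at day 100 of a break.

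- If the participant later resumes, the last IMP lies in the future. The SAE is inside the window under both wordings.
- If the participant never resumes, and this becomes clear only after day 100, the SAE is outside under 13.18 (100 > 60). It is inside under 14.3, because treatment had not ended on day 100. Section 14.3 does not say whether the end is back-dated to the last capsule.

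An SAE must reach the CTRU within 24 hours, when the site cannot yet know which case applies. Such breaks are foreseeable: 12.2.4 lets a break run until a chemotherapy course is complete, and 13.5 expects that some adjuvant courses may still be running at the 6-month scan.

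**3. Size of the possible distortion.** The protocol gives no figure to reproduce here, and no stopping or SAE rates by arm. The inputs are:

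- 60 days, taken as 2 months (13.18, 14.3);
- planned treatment *F* of 24 to 48 months after resection (12.1);
- share stopping early *p* and month of stopping *t*: assumed;
- SAE rate: assumed constant and equal in both arms.

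Mean SAE window per participant = (1 − *p*)(*F* + 2) + *p*(*t* + 2). With equal true rates, the ratio of SAEs per participant equals the ratio of mean windows.

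With *F* = 48 and *t* = 6:

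- *p* = 0.15: 0.85 × 50 + 0.15 × 8 = 43.7 months
- *p* = 0.20: 0.80 × 50 + 0.20 × 8 = 41.6 months; 41.6/43.7 = 0.95
- *p* = 0.25: 0.75 × 50 + 0.25 × 8 = 39.5 months; 39.5/43.7 = 0.90
- *p* = 0.30: 0.70 × 50 + 0.30 × 8 = 37.4 months; 37.4/43.7 = 0.86

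With *F* = 24, comparing 25% with 15%:

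- *t* = 6: (19.5 + 2.0)/(22.1 + 1.2) = 21.5/23.3 = 0.92
- *t* = 12: (19.5 + 3.5)/(22.1 + 2.1) = 23.0/24.2 = 0.95
- *t* = 18: (19.5 + 5.0)/(22.1 + 3.0) = 24.5/25.1 = 0.98

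A separate calculation used *F* of 2 or 4 years and stopping at 3 or 12 months. It gave 0.90 to 0.95 for 20% against 10%, and 0.80 to 0.90 for 30% against 10%. With the same stopping pattern in both arms the ratio is 1.00 throughout.

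**4. Effect of the fix.** Dividing by time under collection gives rate × window / window = rate in each arm. The ratio is then 1.00 whatever the stopping pattern, under the constant-rate assumption.

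**The case against.** The strongest reply is that 13.18 and the visit lists say when participants are asked about AEs, and section 14 says which must be recorded. On that reading AEs and SAEs share one window of treatment plus 60 days. Section 13.9 fits this, since the 60-day call is made only to those still on IMP at visit 10. The window itself is a legitimate choice, and the analysis plan, which is not at hand, may add exposure-adjusted rates. Much of this stands. The reading is plausible, but the protocol does not state it, and a site reading only its visit list would not find the limit. If it is adopted, the AE/SAE mismatch goes and unequal observation time then applies to both. An analysis plan can add person-time rates, but it cannot reconcile what sites were told to collect.

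Three stronger readings are not supported:

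- *A reader might infer that AE collection definitely continues after stopping while SAE collection ceases, so that a late mild event is recorded and a late serious one is not.* Sections 14.3.1 and 14.3.2 contradict the first half. The visit lists ask for any adverse event, and the definition in 14.1 does not exclude serious ones.
- *A reader might infer that late serious bleeding on active drug is lost.* Bleeding is a listed reaction and causality is judged as if the participant were on IPE (12.2.3), so a late bleed judged related is a SAR and stays reportable under 14.3.4. Late deaths are recorded under 13.20.
- *A reader might infer that the SAE comparison is already biased.* The documents give no stopping rates by arm, and equal stopping gives no bias.

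The illustration is also generous to the concern. It gives every non-stopper the full treatment period and ignores deaths, although 18.1.1 assumes 80% control-arm survival at 2 years. It also assumes a constant rate, although surgery is planned within 6 weeks of randomisation (13.4), before any of the assumed stopping times. Perioperative SAEs would thus be captured in both arms, which pulls the ratio towards 1.

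**Conclusion.** The point holds as an inconsistency with a conditional consequence. The AE/AR limit in 14.3.1 and 14.3.2 conflicts with 13.18, the visit lists and Appendix A. The SAE clock has two definitions, which separate for a break of more than 60 days that becomes permanent. The events affected are mainly unrelated, non-fatal SAEs and off-treatment AEs.

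With rates per participant as 19.5 states them, more stopping in one arm would lower its apparent SAE rate. Under equal, constant true rates and assumed early stopping of 20-30% against 15%, the ratio is about 0.86 to 0.95. For 25% against 15% with 24 months of treatment and stopping at month 12 or 18, it is about 0.95 to 0.98. It is 1 if stopping is equal. These figures show a mechanism and are not a forecast for this trial. The case for change is that a modest possible bias and a real ambiguity for sites can be removed cheaply.

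**What to change.** 1. Reconcile 13.18, the visit lists in 13.5 to 13.8, Appendix A and 14.3 to a single AE/SAE window whose 60 days run from one defined point. State how breaks are handled, both those followed by resumption and those that become permanent. Flag any event recorded outside the window as off-treatment. Keep the existing provisions for late SARs, SUSARs and deaths.
2. In 19.5, report AE and SAE rates per person-time within that window by arm, beside the per-participant counts. Keep both: if SAEs cluster around surgery, a crude person-time rate tends to run higher in the arm with more early stopping, so neither measure is sufficient alone.

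The cost is protocol wording, one extra column in the safety tables, and a check that the CRFs capture the date of the last dose. Section 12.2.1 has the duration and reason of breaks recorded, but the protocol does not say that the Withdrawal CRF holds a last-dose date.

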13.19 Pregnancies

Although non-clinical studies have demonstrated no reproductive or developmental toxicity relating to EPA supplementation, there have been no formal studies on the effect of EPA on human reproductive or developmental toxicity. Therefore women of childbearing age and men with partners of childbearing potential must use effective contraceptive measures for the duration of trial treatment and for 60 days following permanent cessation of trial treatment.

All pregnancies and suspected pregnancies (in a trial participant or their partner) occurring from the date of randomisation to the telephone call at 60 days after the end of trial treatment must be reported to the CTRU by completing the Notification of Pregnancy CRF which must be faxed or sent via secure email to the CTRU **within 7 days** of the site becoming aware of the pregnancy.

All trial participants who become pregnant during trial participation must discontinue trial treatment immediately.

The CTRU will report all pregnancies occurring during trial treatment to the Sponsor and all pregnancies will be followed-up until the outcome is known.

13.20 Deaths

All deaths occurring from the date of randomisation to the telephone call 60 days after the end of trial treatment must be recorded on the Notification of Death CRF and faxed or sent via secure email to the CTRU **within 24 hours** of the site becoming aware of the death.

Deaths occurring more than 60 days after the end of trial treatment but during trial follow-up must also be recorded on the Notification of Death CRF but may be returned as per standard data management processes.

13.21 Protocol Deviations and Violations

The CTRU undertake to adopt all reasonable measures to record data in accordance with the protocol. Under practical working conditions, however, some minor variations may occur due to circumstances beyond the control of the CTRU. All such deviations will be documented in the study records, together with the reason for their occurrence; where appropriate, deviations will be detailed in the published report.

13.22 End of follow up phase and End of Trial

The end of the intervention and follow-up phases of the trial is defined as the date when the last participant recruited has reached 2 years post-surgery or randomisation (if that individual

was randomised but didn't undergo surgery). The end of the EMT2 trial will occur at the date of the collection of the last participant's last data item.

13.23 Trial Data and Documentation held at sites

Participating sites must maintain essential trial documentation in an Investigator Site File and a Pharmacy Site File, which will be provided by the CTRU. It is the responsibility of the site staff to ensure these files are properly maintained during the trial and archived according to the Sponsor requirements at the end of the trial (see Section 23 on archiving).

13.24 Case Report Forms (CRFs)

Data will be recorded by site research staff on trial-specific paper CRFs. The originals will be submitted by post to the CTRU within two weeks of the data being collected, and photocopies of the completed CRFs will be held at site. A number of CRFs require expedited reporting to the CTRU:

- Within 24 hours of the research team becoming aware: SAE and SAR CRFs, Death CRFs, Withdrawal CRFs (to the CTRU)
- Within 7 days of the research team becoming aware: Notification of Pregnancy (to the CTRU)

Only the participant's trial number, date of birth and initials will be added to the CRFs.

Participating centre staff are responsible for ensuring the CRFs returned to CTRU do not contain any other personal identifiable data (with the exception of the participant's NHS number which will be recorded at baseline). Following receipt of the completed CRFs, the CTRU will contact sites to resolve any missing or discrepant data.

It is the responsibility of the site to ensure all photocopies of the completed CRFs are appropriately maintained at site during the trial (including any amendments) and archived according to the Sponsor requirements at the end of the trial (see Section 23 on archiving).

13.25 Safety Monitoring Plan

See Appendix C.

14. Pharmacovigilance

14.1 General Definitions

'Adverse Event' (AE) – any untoward medical occurrence in a patient or clinical trial subject administered a medicinal product and which does not necessarily have a causal relationship with this treatment.

An AE can therefore be any unfavourable and unintended sign (including an abnormal laboratory finding, for example), symptom or disease temporarily associated with the use of a medicinal product, whether or not considered to be related to the medicinal product.

‘Adverse Reaction’ (AR) – all untoward and unintended responses to an investigational medicinal product related to any dose administered. This definition implies a reasonable possibility of a causal relationship which is supported by facts, evidence or arguments to suggest a causal relationship. This definition includes medication errors and uses outside what is foreseen in the protocol (i.e. if an AR occurs as a result of a medication error and including misuse and abuse of the product).

‘Serious Adverse Event’ (SAE) – any untoward medical occurrence or effect that at any dose:

- results in death,
- is life-threatening,
- requires hospitalisation or prolongation of existing hospitalisation,
- results in persistent or significant disability or incapacity,
- is a congenital anomaly or birth defect,
- jeopardised the subject or required intervention to prevent one of the above.

These characteristics/consequences have to be considered at the time of the event. For example, regarding a life-threatening event, this refers to an event in which the subject was at risk of death at the time of event; it does not refer to an event which hypothetically might have caused death if it were more severe. Medical and scientific judgement must be exercised in deciding whether an event is ‘serious’ in accordance with these criteria.

‘Serious Adverse Reaction’ (SAR) – reference is made to the criterion of ‘Seriousness’ above in relation to SAE. Where an SAE is deemed to have been related to any IMP used in this trial the event is termed as a serious adverse reaction (Any suspected transmission via a medicinal product of an infectious agent is also considered a serious adverse reaction.)

‘Suspected Unexpected Serious Adverse Reaction’ (SUSAR) – means an adverse reaction, the nature and severity of which is not consistent with the applicable product information:

- in the case of a product with a marketing authorisation, in the summary of product characteristics for that product,
- in the case of any other investigational medicinal product, in the investigator’s brochure relating to the trial in question.

The term 'severity' is used here to describe the intensity of a specific event. This has to be distinguished from the term 'serious'. Reports which add significant information on the specificity, increase of occurrence, or severity of a known, already documented serious adverse reaction constitute unexpected events.

